3.1 Study design

[figure not shown]
This is a blinded, randomized, dose and regimen finding trial utilizing a 3 treatment cohort design where active TIP doses or placebo in addition to the local standard care within each cohort are delivered once or twice daily. Approximately 180 eligible patients will be randomized to one out of the 3 cohorts in a ratio of 1:1:1. The patients within each cohort will be randomized to blinded TIP or placebo with the following randomization scheme: TIP: TIP/placebo cyclical: placebo, in a 2:2:1 ratio. In total, the study has nine treatment arms distributed among the 3 cohorts (see [Section 5.1](#)). Total duration of the study is expected to be up to 196 days with a total of 9 visits, consisting of up to 28 days for the screening epoch; after randomization a 112-day treatment epoch with 6 clinic visits, followed by a 56-day follow-up epoch with 2 clinic visits. Patients will be assessed for safety, tolerability and efficacy (see Assessment Schedule [Table 6-1](#)).

At an initial screening visit (Visit 1), informed consent will be obtained before any study related assessment or procedures are performed, inclusion/exclusion criteria will be assessed and current medications reviewed. All patients signing informed consent must be registered in the Interactive Response Technology (IRT). The patients will commence a flexible 7-28 day screening epoch where all screening assessments will be performed and the presence of pulmonary bacterial colonization with *P. aeruginosa* based on sputum culture will be done. Patients who are otherwise eligible may be re-tested for *P. aeruginosa* in the sputum and/or laboratory evaluations during the screening epoch. Any patient can be re-screened once until enrollment has completed. Patients who had an exacerbation during the screening phase can be re-screened twice until recruitment has been completed. The *P. aeruginosa* bacterial load estimation will be done by quantitative identification using standard culture methods ([Patel et al 2002](#)). [REDACTED]. At

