4.1 Inclusion criteria

Patients/subjects eligible for inclusion in this study must fulfill **all** of the following criteria:

1. Written informed consent must be obtained before any assessment is performed.
2. Male and female patients of ≥ 18 years of age at screening (Visit 1).

3. Proven diagnosis of non-CF BE as documented by computed tomography or high-resolution computed tomography and as assessed by the investigator.
4. At least 2 or more exacerbations treated with oral antibiotics OR 1 or more exacerbation requiring parenteral antibiotic treatment within 12 months prior to screening.
5. $FEV_1 \geq 30\%$ predicted at screening (Visit 1).
6. A stable regimen of local standard treatment for BE (treatments unchanged for 28 days prior to randomization).
7. *P. aeruginosa*, must be documented in a respiratory sample (expectorated sputum, deep-throat cough swab, oro-pharyngeal swab, broncho-alveolar lavage) at least 1 time within 12 months (at least 28 days prior to Visit 1) and also present in the expectorated sputum culture at Visit 1.
8. Must be known sputum producers with a history of daily expectoration.
9. Able to use the T-326 Inhaler as instructed in the protocol in the opinion of the investigator.
10. Clinically stable pulmonary status in the opinion of the investigator.
11. Patients performing daily airway clearance.

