Baseline data (using a specific CRF as necessary) such as spirometry, previous hospital admissions and exacerbations, baseline Medical Research Council (MRC) breathlessness score, colonization with *P. aeruginosa* and other organisms, and radiological changes will be collected for calculation of the Bronchiectasis Severity Index (BSI) for all patients. The BSI will serve as a disease-specific severity assessment tool ([Chalmers et al 2014](#)).

Previous medication to be listed includes information for all antibiotics and macrolides administered within the last 12 months prior to Visit 1.

A sputum sample is required to be collected at Visit 1, cultured locally at the site and tested for the presence of *P. aeruginosa*, to ensure patients meet the inclusion criteria.

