6.4.1 Microbiological assessment

Sputum [REDACTED] will be collected in sterile containers before study drug administration at all treatment epoch and follow-up epoch visits. The [REDACTED] sputum specimen will be used to culture for the presence of *P. aeruginosa* (quantitative test)

[REDACTED] Following alternatives can be chosen, if a patient is unable to expectorate during the visit:

- Sputum will be induced at the baseline visit (Visit 2) as the [REDACTED] specimen.
- At the other visits, a deep-throat cough swab will be collected for non-sputum producing patients for microbiology specimens. Deep-throat cough swab specimens will be evaluated semi-quantitatively.
- Patients may undergo a short physiotherapy session at any visit, if feasible, to enable to expectorate spontaneously.

[REDACTED]

[REDACTED]

[REDACTED]

Microbiological analyses, [REDACTED], will be performed centrally at a qualified microbiology laboratory. Details on the collection and shipment of samples, generation of data and reporting of results by the microbiology laboratory are provided in a separate laboratory manual.

[REDACTED]

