2.5.2 Statistical hypothesis, model, and method of analysis

The comparisons of 3 doses of active treatment (TIP 3 capsules OD, 5 capsules OD, and 4 capsules BID) versus pooled placebo will be evaluated by testing the following null hypothesis (H₀) versus the alternative hypothesis (H_a):

H₀: TIP treatment arm is equal to pooled placebo group in bacterial load in sputum at Day 29

H_a: TIP treatment arm is not equal to pooled placebo group in bacterial load in sputum at Day 29

The primary efficacy endpoint will be analyzed using the analysis of covariance (ANCOVA) model. The model will contain treatment, baseline CFU (in log₁₀ unit), and baseline macrolide use (yes/no). The adjusted means will be displayed together with the associated standard error and 2-sided 95% CI. Pairwise comparisons of TIP dosing groups will be conducted versus placebo. To control the family-wise type-I error rate (3 dose levels vs. placebo) at the 2-sided 5% significance level, the step-wise Dunnett procedure will be used.

For the primary efficacy analysis, patients from treatment arms TIP and TIP/placebo cyclical regimen will be pooled for each cohort. This is possible because all patients within the same cohort on the TIP treatment arms (cyclical or continuous) are receiving the same treatment during the first 28 days. Placebo patients will be pooled across the 3 cohorts, as the number of placebo capsules is not expected to influence the change in *P. aeruginosa* bacterial counts.

The estimated adjusted treatment difference (TIP – placebo) will be displayed along with the associated standard error, 2-sided 95% CI, and p-value (2-sided).

The estimated treatment difference and CI will be displayed in forest plot for the treatment arms TIP and TIP/placebo cyclical regimen pooled for each cohort vs pooled placebo across 3 cohorts.

For other efficacy analyses up to and including Day 29, patients from treatment arms TIP and TIP/placebo cyclical regimen will be pooled for each cohort; placebo patients will be pooled across the 3 cohorts.

If no *P. aeruginosa* isolated (NPAI) are detected, i.e, no growth detected, at a given visit where the laboratory sample was available at that visit, the value will be imputed as 99 based on the lower limit of detection (dilution factor is currently 1/100). Log 10(99) will be used in the analysis.

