2.6.1 Secondary endpoints

2.6.1.1 *P. aeruginosa* colony forming units (CFU)

Anti-microbial efficacy of TIP versus placebo over the entire study duration, as measured by the absolute change in log₁₀ CFUs of *P. aeruginosa* in sputum from baseline to each post-baseline visit (Visits 102 (Day 8), 103 (Day 29), 104 (Day 57), 105 (Day 85) and 106 (Day 113)), will be assessed by morphotype and sum of all morphotypes (mucoid, dry, small colony-variants). For patients with a negative *P. aeruginosa* result, i.e, NPAI, the quantitative test result for the analysis will be imputed for each morphotype with log (99) as this represents the detection level for a dilution of 100. Means together with the 95% CIs will be graphically displayed over time. The summaries will be provided by treatment groups Cohort A: TIP, Cohort A: TIP/placebo cyclical, Cohort B: TIP, Cohort B: TIP/placebo cyclical, Cohort C: TIP, Cohort C: TIP/placebo cyclical, Pooled TIP and Pooled TIP/placebo cyclical and pooled placebo. Comparisons between treatment regimens across all cohorts versus pooled placebo will also be analyzed.

The number and percentage for patients with no *P. aeruginosa* in sputum and number and percentage of patients with a positive result of *P. aeruginosa* in sputum will be tabulated by cohort, treatment arm, pooled arms by continuous and cyclic regimens and visit. Percentages will be based on the number of patients for whom microbiology results exist per visit.

The number and percentage of patients with NPAI at 2 consecutive post-baseline visits will also be presented by cohort and treatment arm, pooled arms by continuous and cyclic regimens.

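### The negative-culture percentages in SAP 2.6.1.1 do not require a positive central baseline culture, so patients already negative before dosing would count as negative on treatment

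*SAP*

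**What the plan says.** **Entry.** Inclusion criterion 7 (Protocol 4.1) asks for *P. aeruginosa* in a respiratory sample "within 12 months (at least 28 days prior to Visit 1) and also present in the expectorated sputum culture at Visit 1". The Visit 1 sample is read at the site for presence only (Protocol 6.2): "A sputum sample is required to be collected at Visit 1, cultured locally at the site and tested for the presence of" the organism. Screening lasts 7 to 28 days, and otherwise eligible patients may be re-tested "in the sputum and/or laboratory evaluations during the screening epoch" (Protocol 3.1). No minimum density is set.

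**Endpoint.** CFU counts come from a different sample and laboratory: pre-dose sputum from Day 1 onward, with analyses that "will be performed centrally at a qualified microbiology laboratory" (Protocol 6.4.1). SAP 2.1.1 takes as baseline the last non-missing result before the first dose. Randomisation is also on Day 1, and nothing visible makes it depend on the central result. The FAS (SAP 2.2) has no baseline-culture condition.

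**Scoring.** For a culture with no growth "at a given visit where the laboratory sample was available at that visit, the value will be imputed as 99" (SAP 2.5.2). The rule has no exception for the baseline visit. The primary ANCOVA has treatment, baseline log10 CFU and macrolide use as main effects.

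**Tables.** SAP 2.6.1.1 tabulates negative and positive patients by visit, with this denominator: "Percentages will be based on the number of patients for whom microbiology results exist per visit". It also counts patients with no *P. aeruginosa* isolated (NPAI) at two consecutive post-baseline visits. Neither summary is conditioned on a positive baseline.

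**The concern.** A patient can be positive locally at Visit 1 and negative centrally on Day 1. That patient met criterion 7, so on the visible text was correctly randomised and stays in the FAS. Two consequences follow.

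First, the negative-culture tables cannot separate a patient who became negative on treatment from one who was negative before the first capsule. A reader of a phase II dose-finding report will tend to read those percentages, especially the two-consecutive-visit one, as a treatment response.

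Second, such a patient starts at the detection floor and can only stay level or rise. If TIP cannot lower the load in these patients, the average treatment difference shrinks. A single baseline slope does not model an effect that disappears at the floor. The sensitivity analyses in SAP 2.5.4 (Mann-Whitney-Wilcoxon and the per-protocol set) are not aimed at this.

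**Working it through.** **Inputs from the documents.** Difference 2.0 and SD 2.0 log10 CFU/g, two-sided alpha 0.05/3, 20% discontinuation (Protocol 9.7, SAP 3). Pooled placebo 36, and 24 + 24 = 48 TIP patients per dose (Protocol 3.2). 107 of 180 randomised (SAP 1). Eradication of 35% on nebulised tobramycin in the cited double-blind pilot (Protocol 1.1). The baseline-negative share f is not given; 5%, 10% and 20% are assumptions.

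**1. The plan's own figures.** A two-sample t test needs 29 evaluable patients per group for 90% power, and 29/0.8 = 36.25 against the stated 36. With 36 × 0.8 = 28.8 placebo and 48 × 0.8 = 38.4 TIP patients, the standard error is 2.0 × √(1/28.8 + 1/38.4) = 0.493 and the noncentrality is 2.0/0.493 = 4.06. Power is 94.2% against the stated 94%. The sample-size figures are reproduced.

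**2. The floor.** log10(99) = 1.996. A patient with this baseline has a change of zero or more.

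**3. Negative-culture percentages.** With 107 patients, each active arm has about 107 × 1/3 × 2/5 = 14.3 patients and pooled placebo about 107/5 = 21.4. One patient is 1/14 = 7.1 points in an active arm and 1/21.4 = 4.7 points in pooled placebo. Compared with a baseline-positive denominator, the rise from one baseline-negative patient who stays negative, in an arm of 14 with k converters, is (k + 1)/14 − k/13. This is 7.1 points at k = 0 and 42.9% − 38.5% = 4.4 points at k = 5, so 7 points is the upper end.

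As an illustration, take 35% becoming negative on TIP, an assumed 0% on placebo, and baseline-negatives staying negative. The tabulated percentage is (1 − f) × true rate + f:

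| f | TIP | Placebo | Difference |
|---|---|---|---|
| 0 | 35.0% | 0% | 35.0 |
| 5% | 38.2% | 5% | 33.2 |
| 10% | 41.5% | 10% | 31.5 |
| 20% | 48.0% | 20% | 28.0 |

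Each arm's percentage rises while the contrast shrinks by the factor (1 − f).

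**4. Primary effect, worst case.** Assume no treatment effect in baseline-negatives, so the mean difference is 2.0(1 − f), with the SD held at 2.0. The restricted analysis keeps 2.0 but has n(1 − f) patients. Power, with 20% loss throughout:

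| f | Difference | FAS, 180 | Baseline-positive, 180 | FAS, 107 | Baseline-positive, 107 |
|---|---|---|---|---|---|
| 0 | 2.0 | 94.2% | 94.2% | 73.1% | 73.1% |
| 5% | 1.9 | 91.5% | 92.9% | 67.9% | 70.3% |
| 10% | 1.8 | 88.0% | 91.3% | 62.3% | 67.3% |
| 20% | 1.6 | 78.2% | 87.1% | 50.5% | 60.6% |

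**5. Primary effect under ANCOVA.** A simulation with an assumed mean baseline of 7 log10, a true effect of 2.0 and the floor at 1.996 recovers about 1.96 at f = 0. At f = 5%, 10% and 20% the estimated effect is:

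- 1.86, 1.77 and 1.57 if baseline-negatives are still negative at Day 29;
- 1.91, 1.87 and 1.77 if half are;
- 1.96, 1.95 and 1.95 if the negative baseline was a sampling miss and they otherwise behave like the rest.

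**The case against.** The strongest reply is that such patients should be few. Criterion 7 requires two positives, and re-testing at screening does not remove the need for the earlier one. Patients must be daily sputum producers (criterion 8). Inhaled and systemic anti-pseudomonal antibiotics are excluded for 28 days before dosing (exclusions 26 and 27). Sputum is induced at baseline if the patient cannot expectorate. All this stands. A reader might infer that one positive sample is enough for entry, so that intermittent carriers enter freely; criterion 7 does not support that. Still, none of these rules guarantees central growth on Day 1.

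Second, dilution is not a given. The hypothesis concerns load at Day 29. With baseline as a covariate, analysing the change or the Day 29 value gives the same treatment estimate. A baseline-negative patient whose load returns on placebo but stays suppressed on TIP adds to the difference. This stands too, and step 5 shows it. The SAP also says that, after the early stop at 107, inferential results can be treated as exploratory, so loss of power at 180 patients is not the main consequence.

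Third, a reader might infer that the tables flatter TIP against placebo. They do not: where baseline-negatives persist equally in all arms, the contrast shrinks. The SAP also does not call the measure clearance, and everyone with a result is the right denominator for prevalence at a visit. That defence does not fit a summary of two consecutive post-baseline negatives as well.

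Fourth, the by-visit table is not limited to post-baseline visits and may already show baseline-negative counts. SAP Tables 5-4 and 5-5 (exclusions and patient classification) are listed but not visible, so exclusion from the per-protocol set cannot be ruled out. The primary analysis uses the FAS in either case.

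**Conclusion.** The gap is real and modest. On the visible text, a patient with a negative central culture on Day 1 is kept in the FAS, scored at the floor, and counted among the negatives after baseline. If such patients stay negative, each arm's absolute percentage is too high and the TIP-placebo contrast is too small. How large this is depends on f, which the documents do not give.

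The effect on the primary endpoint is only a possibility. The power figures of 92%, 88% and 78% are a worst case at the planned 180 patients, with no effect in baseline-negatives and an unchanged SD; if the negative baseline is a sampling miss there is almost no loss. The documents do not support saying that the primary effect is diluted as a matter of fact, or that the sample-size calculation is wrong.

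**What to change.** In SAP 2.6.1.1, base the post-baseline negative-culture percentage and the two-consecutive-visit NPAI percentage on patients with a positive central baseline culture. The by-visit prevalence over all patients with a result may stay alongside, labelled as such. State the number baseline-negative by arm, unless the by-visit table already gives it.

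Keep the FAS primary analysis unchanged. Optionally, repeat the primary ANCOVA in FAS patients with a positive central baseline as a supportive analysis. Baseline status is fixed before dosing, so the subset does not depend on treatment.

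The cost is a few lines of SAP text and, if the option is taken, one rerun on existing data. Denominators become slightly smaller.

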2.6.1.2 Pulmonary exacerbations

Patients with pulmonary exacerbations (pulmonary exacerbation is defined in [\[Section 6.4.4 of the protocol\]](#) will be categorized into the following:

- Category 1: pulmonary exacerbations requiring oral antibiotics only
- Category 2: pulmonary exacerbations requiring parenteral antibiotics and/OR pulmonary exacerbation requiring hospitalization

A patient could be counted in more than 1 exacerbation category.

In addition to the antibiotics listed in Appendix 12 of the protocol, concomitant medication data will be reviewed on an ongoing basis. A list identifying all relevant antibiotics used for the treatment of pulmonary exacerbations will be provided prior to database lock.

Pulmonary exacerbations requiring hospitalization will be identified from the adverse event – pulmonary exacerbations eCRF data.

The following pulmonary exacerbation-related parameters over the treatment epoch (through Day 113) and the study period (unless otherwise stated) will be summarized by cohort and treatment arm. In addition, data will also be pooled and summarized for all three continuous TIP regimens together and all three cyclic TIP regimens together.

- The proportion of patients with at least 1 pulmonary exacerbation overall and by exacerbation category
- Number of pulmonary exacerbations overall and by exacerbation category
- Time to first pulmonary exacerbation overall and by exacerbation category for overall study period
- The exposure adjusted rate of pulmonary exacerbations overall
- Duration of pulmonary exacerbations in days by exacerbation category
- Time to permanent study drug discontinuation due to pulmonary exacerbation for overall study period
- The proportion of patients who permanently discontinued study drug due to pulmonary exacerbation

In addition, the pulmonary exacerbation signs and symptoms lasting for more than 24 hours and 48 hours, respectively, will be summarized separately (see [section 2.6.3.2](#)).

2.6.1.3 Anti-pseudomonal antibiotics

The following anti-pseudomonal antibiotics-related parameters will be assessed by cohort and treatment arm and also by pooled three continuous TIP regimens and pooled three cyclic TIP/placebo regimens.

[figure not shown]
- Proportion of patients requiring anti-pseudomonal antibiotics (overall, oral, parenteral)
- Time to first use of anti-pseudomonal antibiotics across the entire study period
- The exposure adjusted rate of usage of anti-pseudomonal antibiotics across the entire study period
- Duration of anti-pseudomonal antibiotic use across the entire study period

Anti-pseudomonal antibiotics will be identified prior to database lock.

2.6.1.4 Hospitalization

The following hospitalization-related parameters will be assessed by cohort and treatment arm, by pooled three continuous TIP regimens and pooled three cyclic TIP/placebo regimens:

- Time to first hospitalization due to serious respiratory-related AEs across the entire study period
- Duration of hospitalization due to serious respiratory-related AEs across the entire study period
- Number of hospitalizations due to serious respiratory-related AEs across the entire study period
- Proportion of patients requiring hospitalization due to serious respiratory-related AEs across the entire study period

2.6.3 Statistical hypothesis, model, and method of analysis

In general, unless otherwise specified, the following 6 pairwise comparisons will be performed for the secondary endpoints at the 5% significance level without multiplicity adjustment, wherever an inferential analysis is specified:

- TIP 3 capsules OD versus pooled placebo
- TIP/placebo cyclical 3 capsules OD versus pooled placebo
- TIP 5 capsules OD versus pooled placebo
- TIP/placebo cyclical 5 capsules OD versus pooled placebo
- TIP 4 capsules BID versus pooled placebo
- TIP/placebo cyclical 4 capsules BID versus pooled placebo

Descriptive summary statistics by cohort, treatment arm, pooled treatment arm by regimen and pooled placebo will be provided where applicable.

In addition, data will also be summarized for selected endpoints, by pooling continuous TIP regimens together (i.e. TIP 3 capsules OD. from Cohort A + TIP 5 capsules OD from Cohort B+ TIP 4 capsules BID from cohort C) and pooling cyclic TIP regimens together (i.e. TIP/placebo cyclical 3 capsules OD from Cohort A + TIP/placebo cyclical 5 capsules OD. from Cohort B+ TIP/placebo 4 capsules BID cyclical from cohort C) vs pooled placebo.

In addition, the following 2 pairwise comparisons will be performed for the selected endpoints at the 5% significance level without multiplicity adjustment:

- Pooled TIP continuous regimens versus pooled placebo
- Pooled TIP/placebo cyclical regimens versus pooled placebo.

Forest plot will be plotted for below endpoints in addition to the primary endpoint for each treatment arm across 3 cohorts compared with pooled placebo separately and also for the comparison between pooled TIP continuous (pooled from 3 cohorts) with pooled placebo and for

the comparison between pooled TIP/placebo cyclic (pooled from 3 cohorts) with pooled placebo.

- LS Mean difference in log₁₀ CFUs of *P. aeruginosa* in sputum and CI
- For exposure adjusted rate and CI of pulmonary exacerbations during the study
- For incident rate ratio and CI for anti-pseudomonal antibiotics during the study
- Incident rate ratio and CI hospitalization due to serious respiratory-related AEs across the entire study period
- LS Mean difference in QoL-B RSS and CI

2.6.3.1 *P. aeruginosa* colony forming units (CFU)

The primary efficacy parameter (CFU) will be analyzed using a similar ANCOVA model as used in primary efficacy analysis at Day 85, Day 113 and Day 169. The model will contain treatment, baseline CFU (in log₁₀ unit), and baseline macrolide use (yes/no).

The analysis will not be performed by the subgroup of morphotypes. Six pairwise comparisons will be evaluated as specified in [Section 2.6.3](#). The estimated adjusted treatment difference for each of the 6 comparisons (TIP–placebo) will be displayed along with the associated standard error, 2-sided 95% CI. In addition, CFU data will be summarized by morphotype and sum of all morphotypes at each scheduled visit.

